### **Adverse Reactions Leading to Discontinuation**

The discontinuation rate due to adverse reactions was 13% among patients treated with 100 mg ADDYI at bedtime and 6% among patients treated with placebo. Table 1 displays the most common adverse reactions leading to discontinuation in four trials of premenopausal women with HSDD.

**Table 1: Adverse Reactions\* Leading to Discontinuation in Randomized, Double-blind, Placebo-controlled Trials in Premenopausal Women with HSDD**

	PLACEBO (N=1556)	ADDYI (N=1543)
Dizziness	0.1%	1.7%
Nausea	0.1%	1.2%
Insomnia	0.2%	1.1%
Somnolence	0.3%	1.1%
Anxiety	0.3%	1%

\*Adverse reactions leading to discontinuation of > 1% of patients receiving 100 mg ADDYI at bedtime and at a higher incidence than placebo-treated patients.

### **Most Common Adverse Reactions**

Table 2 summarizes the most common adverse reactions reported in four trials of premenopausal women with HSDD. This table shows adverse reactions reported in at least 2% of patients treated with ADDYI and at a higher incidence than with placebo [see **WARNINGS AND PRECAUTIONS**]. The majority of these adverse reactions began within the first 14 days of treatment.

**Table 2: Common Adverse Reactions\* in Randomized, Double-blind, Placebo-controlled Trials in Premenopausal Women with HSDD**

	PLACEBO (N=1556)	ADDYI (N=1543)
Dizziness	2.2%	11.4%
Somnolence	2.9%	11.2%
Nausea	3.9%	10.4%
Fatigue	5.5%	9.2%
Insomnia	2.8%	4.9%
Dry mouth	1.0%	2.4%

\* Adverse reactions reported in ≥ 2% of patients receiving 100 mg ADDYI at bedtime and at a higher incidence than placebo-treated patients.

### ***Less Common Adverse Reactions***

In four trials in premenopausal women with HSDD treated with 100 mg ADDYI at bedtime, less common adverse reactions (reported in  $\geq 1\%$  but  $< 2\%$  of ADDYI-treated patients and at a higher incidence than with placebo) included:

- Anxiety (ADDYI 1.8%; placebo 1.0%),
- Constipation (ADDYI 1.6%; placebo 0.4%),
- Abdominal pain (ADDYI 1.5%; placebo 0.9%),
- **Metrorrhagia** (ADDYI 1.4%; placebo 1.4%),
- Rash (ADDYI 1.3%; placebo 0.8%),
- Sedation (ADDYI 1.3%; placebo 0.2%), and
- **Vertigo** (ADDYI 1%; placebo 0.3%).

### ***Appendicitis***

In the five trials of premenopausal women with HSDD, **appendicitis** was reported in 6/3973 (0.2%) flibanserin-treated patients, while there were no reports of appendicitis in the 1905 placebo-treated patients.

### ***Accidental Injury***

In five trials of premenopausal women with HSDD, accidental injury was reported in 42/1543 (2.7%) ADDYI-treated patients and 47/1905 (2.5%) placebo-treated patients. Among these 89 patients who experienced injuries, 9/42 (21%) ADDYI-treated patients and 3/47 (6%) placebo-treated patients reported adverse reactions consistent with CNS depression (e.g., **somnolence**, fatigue, or sedation) within the preceding 24 hours.

Source: <http://www.rxlist.com/addyi-side-effects-drug-center.htm>

**13. Monitoring of Safety:**

A researcher will be present with participants during the duration of the experiment. While participants are in a separate room sheltered from electrical interference for EEG recording, researchers will monitor participants' well-being via cameras and microphones within this room. Participants will have the ability to communicate with researchers through these microphones and may opt out of participation at any time. Participants will also be provided with the IRB's contact information on the consent form, and we will contact IRB should any adverse effects occur.

Participants will be advised not to drive, operate machinery, or do things that require clear thinking until at least 6 hours after taking flibanserin and until they know how flibanserin affects them. This has been addressed in the informed consent and will be discussed with participants.

Regarding Addyi's side effects: Subjects will be directed to call a member of the study team if they believe they are experiencing any side effects.

Vital signs (blood pressure, pulse, respiratory rate, temperature, height, weight) will be obtained at every visit. Orthostatic vital signs will be used in terms of blood pressure and pulse.

No baseline laboratory testing will be done.

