## **6. Duration of Protocol:**

The total duration of the entire study on campus is 4.5 hours maximum. **Visit 1's duration:** 2 hours. Upon receipt of the subject's written consent, the subject will meet with [name] or [name] to have a diagnosis of HSDD confirmed, take a urine pregnancy test, and be asked to fill out questionnaires (duration 45 minutes maximum). Then, an IRB-approved member of the HPEN laboratory will walk the subject to the laboratory where the subject will be completing other questionnaires and performing the behavioral visual task while the subject's brain activity and eye movements are recorded (1h15 minutes maximum, including breaks and time to walk to the laboratory). At the end of Visit 1, a member of the HPEN laboratory will walk the subject to the pharmacy where they will receive either Flibanserin or Placebo. The HPEN member will not know what the patient receives (placebo or Flibanserin). One week after visit 1, a member of the study staff will contact the subject via telephone to see if the subject has experienced any side effects or if the subject has any questions. If any side effects are reported, the study staff will immediately contact [name] or [name] to confirm that any appropriate follow up is provided. **Phone call 2's duration:** 30 minutes. Two weeks after visit 1, the subject will be asked about any side effects she has experienced or is currently experiencing. The subject will also be asked to fill out some of the same questionnaires as visit 1 and answer questions about mood and sexual desire. **Visit 2's duration:** 1 hour. The subject will go directly to the HPEN laboratory, where the subject will perform the behavioral visual task again while the subject's brain activity and eye movements are recorded and fill out the same questionnaires the subject filled out during Visit 1. **Visit 3's duration:** 1 hour. The subject will again go directly to the HPEN laboratory to perform the behavioral visual task while the subject's brain activity and eye movements are recorded and fill out the same questionnaires as Visits 1 and 3.

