## **28. Adverse Events:**

[name], [name], and [name] will be responsible for the detection, documentation, classification, reporting, and follow-up of adverse events, including events meeting the definition of a serious adverse event (SAE). An adverse event (AE) us any undesirable experience associated with the use of a medical product in a patient. For the regulatory definitions of SAEs, refer to

<http://www.fda.gov/Safety/MedWatch/HowToReport/ucm053087.htm>.

All AEs will be recorded regardless of causality or severity. At the minimum, information collected concerning AEs should include the following: onset date, resolution date, severity (i.e., mild, moderate, or severe), relationship to study drug, intervention (if needed), seriousness of the event, and outcome.

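### Section 28 promises to record all adverse events regardless of causality, but every described question or instruction put to the woman about harms asks for side effects, and none is described at Visits 2 or 3

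*Combined protocol and SAP*

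**What the plan says.** Section 28 (Adverse Events) states that "All AEs will be recorded regardless of causality or severity". The information to be collected on each event includes "relationship to study drug, intervention (if needed), seriousness of the event, and outcome". The intended order is therefore capture first and attribution second. The same section defines an adverse event as "any undesirable experience associated with the use of a medical product in a patient" and does not say whether the association is one of time or of cause.

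Section 6 (Duration of Protocol) describes the planned contacts. The first call comes a week into treatment, when "a member of the study staff will contact the subject via telephone to see if the subject has experienced any side effects". This call also invites her own questions. At the second call, two weeks after Visit 1, "the subject will be asked about any side effects she has experienced or is currently experiencing", and she also answers questions about mood and sexual desire. For Visit 2 the text reads: "The subject will go directly to the HPEN laboratory, where the subject will perform the behavioral visual task again". EEG, eye tracking and questionnaires complete that visit, and Visit 3 is described in the same way. Neither description contains a question about adverse events.

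Section 13 (Monitoring of Safety) covers the time between contacts, in a paragraph about the side effects of Addyi: "Subjects will be directed to call a member of the study team if they believe they are experiencing any side effects". It also provides for vital signs at every visit, with orthostatic blood pressure and pulse, and for camera and microphone observation while the woman is in the EEG room.

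**The concern.** A promise to record events whatever their cause is only as good as the question that brings them to light. To ask for side effects is to ask the woman to decide first whether the tablets were responsible. If she thinks they were not, she can truthfully answer no, and the event never reaches the person who should rate its relationship to study drug.

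The safety criterion at the end of the Statistical Hypotheses in Section 11 compares flibanserin with placebo on events above mild severity rated possibly, probably or definitely related. The lowest of those ratings is a low bar. A blinded physician might rate a fall or injury during eight weeks of bedtime dosing as possibly related even though the woman saw no link. An event that was never elicited cannot be rated, so it drops out of that comparison and out of any wider account of harms.

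**Working it through.** The point rests on wording, and the plan states no figure to reproduce. The check compares every described source of safety information with the promise in Section 28.

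| Source | Section | When | Depends on her linking the event to the tablets? |
|---|---|---|---|
| First call | 6 | Week 1 | Yes, as worded (side effects, or any questions) |
| Second call | 6 | Week 2 | Yes, as worded (side effects); mood is asked separately |
| Call she starts herself | 13 | Any time | Yes, explicitly: her belief is the trigger |
| Visits 2 and 3 | 5 and 6 | Weeks 4 and 8 | No adverse event question described |
| Vital signs, orthostatic measures | 13 | Every visit | No, but visit time only |
| Camera and microphone | 13 | During EEG | No, but EEG time only |
| Pill count | 24 | Next visit | No, but measures missed doses, not events |

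**Coverage in time.** The last described question about harms is at week 2 of 8. That leaves 8 − 2 = 6 weeks, or 6/8 = 75% of treatment, in which the only described report route is the belief-triggered call. Of the four planned contacts after dispensing (two calls and two visits), two carry a harms question and two do not.

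**Scale, as an illustration only.** Accidental injury is an event that a woman may not call a side effect. Inputs from Section 12 (Accidental Injury): 42/1543 = 2.7% on flibanserin and 47/1905 = 2.5% on placebo. Arm size from Section 5: 60.

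- Expected injuries with full capture: 60 × 42/1543 = 1.6 on flibanserin and 60 × 47/1905 = 1.5 on placebo.
- Chance of recording at least one injury on flibanserin if a share c of injuries is captured: 1 − (1 − c × 42/1543)^60.

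| Capture share c (assumed) | Expected recorded on flibanserin | Chance of at least one |
|---|---|---|
| 100% | 1.6 | 81% |
| 80% | 1.3 | 73% |
| 60% | 1.0 | 63% |
| 40% | 0.7 | 48% |

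The capture shares are assumptions, since the documents give none. The injury rates come from 24-week trials in premenopausal women. They are an upper guide for eight weeks, and this trial also enrols postmenopausal women. The table shows only that, with so few events expected, partial capture can decide whether a kind of harm is seen at all.

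**The case against.** The strongest reply is that side effects may be lay shorthand. A narrative protocol is not a call script, and no script is shown. The first call also invites any questions. Sections 7 and 19 and the consent form were not in the text available, so a fuller procedure there cannot be excluded. This limits confidence. Even so, the same term appears in all three report routes, and Section 13 ties it both to Addyi and to the woman's belief. Where the promise is free of causality, the question should be too.

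Second, not everything depends on her attribution. Vital signs and observation do not, and this stands. They cannot, however, reveal an event at home between visits.

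Third, many events would still surface. Mood is asked about at week 2, and the Hamilton scale in Section 5 is a repeated outcome. Section 12 lists abdominal pain, dizziness and syncope among the known effects, so a woman told of them would be expected to report them. This also stands. The gap concerns injuries, illnesses and medical visits without an obvious listed symptom.

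Fourth, the definition in Section 28, read with the words on causality that follow it, need not be causal. That is a fair reading. The phrase is ambiguous rather than wrong.

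A reader might go further and infer that the wording biases the comparison between arms, because dizziness (11.4% v 2.2%) and somnolence (11.2% v 2.9%) in Table 2 could reveal the assignment and lead women on flibanserin to blame the tablets more often. Section 12 might seem to support this: among injured patients, "9/42 (21%) ADDYI-treated patients and 3/47 (6%) placebo-treated patients reported adverse reactions consistent with CNS depression". But those figures record preceding symptoms, not what anyone attributed or reported. The documents give no attribution rate in either arm, and the Section 11 criterion counts only related events above mild severity, so extra reports of mild or unrelated events would not enter it if rated correctly.

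**Conclusion.** The described questions do not deliver what Section 28 promises. Every described question or instruction put to the woman about harms asks for side effects, and no adverse event question is described at Visits 2 or 3. Followed as written, the plan can miss events at home that she does not link to the tablets before relatedness is rated. The expected direction is under-capture in both arms. The amount cannot be derived from the documents, and a difference in capture between arms remains a possibility that they do not quantify.

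The conclusion assumes that the calls follow the wording of Section 6 and that no further adverse event procedure stands in the sections and consent form that could not be read. It calls for a modest, inexpensive improvement and does not invalidate the safety data.

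**What to change.** - **Both calls and Visits 2 and 3 (Section 6):** ask an open question that does not mention cause, for example: *Since our last contact, have you had any new or worse health problem, injury or medical visit, whether or not you think the study tablets caused it?* Rewording the two calls alone would leave the last six weeks to self-initiated calls, so the visits must be included.
- **Section 13:** change the instruction on when to call so that it uses the same scope.
- **Section 28:** state that an adverse event is recorded whether or not it is considered related to study drug.
- **Rating:** leave relatedness to the physician, whom Section 25 already keeps blinded.

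The cost is a few minutes at each of four contacts that are already planned, and more unrelated events to log. No new visit, test or staff is needed.

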**14. Payment:**

Participants will receive a parking voucher or \$ 5 for public transportation at the end of every visit. At the end of each visit, participants will also receive \$20 monetary compensation for their participation in the study. At the end of visit 3, participants will receive also receive \$50 monetary compensation for completing the entire study.

**15. Informed Consent:**

Participants will be provided with the consent form attached in this IRB application. Participants must acknowledge understanding of procedures, risks, and benefits by signing this consent form before the study can proceed.

**16. Confidentiality:**

De-identified data will be stored in locked drawers or cabinets or on password-protected computers within the HPEN laboratory or on password protected University of Chicago server, such as UChicago Box. Data may be used in publications, but no personally identifiable information will be disseminated outside of researchers included in this protocol.

**18. Recruiting Methods:**

Subjects will be recruited via Flyers posted on Campus or Obstetrics and Gynecology practices or via ads posted on Craigslist.

**20. Anticipated Coordination between Inter-Departmental Faculty:**

[name]., [name]., and [name]. are all members of the Department of Psychiatry and Behavioral Neuroscience. These researchers will coordinate extensively on this project.

**21. Pregnancy Test:** Conducted at screening visit.

**22. Acceptable forms of birth control:** oral contraceptives (e.g., combined pill or progestin only pill), intrauterine device, shot/injection, partner uses a male condom, vaginal ring, birth control patch, and abstinence.

**Any pregnancy conceived during this study will be followed and its outcome (both maternal and neonatal) will be reported.**

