## **12. Potential Risks and Benefits:**

The study will offer no direct benefits (besides monetary benefits and potential improvement of sexual desire) to participants. The questionnaires, tracking eye-movement, and EEG behavioral task also present minimal risks, which may include boredom and fatigue from looking at pictures for a few minutes during EEG collection and anxiety or discomfort or distress related to responding to questionnaires.

Addyi risks: Addyi (flibanserin) is a multifunctional serotonin agonist and antagonist (MSAA) indicated for the treatment of premenopausal women with acquired, generalized hypoactive sexual desire disorder (HSDD) as characterized by low sexual

desire that causes marked distress or interpersonal difficulty and is NOT due to: a co-existing medical or psychiatric condition, problems within the relationship, or the effects of a medication or other drug substance. The recommended dosage of Addyi is 100 mg taken once daily at bedtime.

**CONTRAINdications:** Alcohol; Moderate or strong cytochrome P450 3A4 inhibitors; Hepatic impairment.

IF THE SUBJECTS ARE A NURSING MOTHER, THEIR PARTICIPATION IS NOT RECOMMENDED.

IF THE SUBJECTS ARE PREGNANT, YOUR PARTICIPATION CANNOT BE ACCEPTED.

**DRUG INTERACTIONS:** Oral contraceptives increase Flibanserin exposures and incidence of adverse effects.

FDA-approved Flibanserin has known side effects we want you to be aware of, such as syncope and Central Nervous System (CNS) depression.

**Other common side effects of Addyi (Flibanserin) include:** dizziness, sleepiness, nausea, fatigue, insomnia, and dry mouth. Other side effects of Addyi include anxiety, constipation, abdominal pain, menstrual spotting, rash, sedation, and spinning sensation (vertigo).

**Addyi may interact with alcohol, CNS depressants (such as diphenhydramine, opioids, hypnotics, benzodiazepines), antifungals, antiviral drugs, grapefruit juice, oral contraceptives, cimetidine, fluoxetine, ginkgo, ranitidine, proton pump inhibitors, selective serotonin reuptake inhibitors (SSRIs), some antibiotics, nefazodone, , ketoconazole, itraconazole, posaconazole, clarithromycin, ritonavir, saquinavir, nelfinavir, indinavir, boceprevir, telaprevir, telithromycin, conivaptan, amprenavir,**

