#### Exclusion:

- Male
- < 21 years-old or > 74 years-old
- Hairstyles that induce artifacts to the EEG recording (i.e. braids, weave, extensions)
- Currently taking psychotropic medication
- Currently pregnant or lactating
- Women who report not being able to stop drinking alcohol during the duration of the study
- History of seizures or neurological disorders
- Under hormonal therapy
- Current or past diagnosis of cancer
- Any unstable medical illnesses
- Lifetime history of bipolar disorder, schizophrenia, or psychotic disorder
- Current or recent (past 3 months) substance abuse or dependence
- Current or recent (past 3 months) clinical depression
- Currently taking any medications that have/may have unfavorable interactions with Flibanserin
- Uncorrected vision
- Hepatic impairment

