**27. Prohibited Medications**

<http://www.fda.gov/Drugs/DevelopmentApprovalProcess/DevelopmentResources/DrugInteractionsLabeling/ucm093664.htm> (refer to section 12 for more information)

The following medications are not to be taken by eligible subjects:

atazanavir; azamulin; buspirone; Clarithromycin; darunavir; dextromethorphan N-demethylation; digoxin; eletriptan; erythromycin N-demethylation; felodipine; indinavir; itraconazole; ketoconazole; lopinavir; lovastatin; midazolam 1-hydroxylation; midazolam; nefazodone; nelfinavir; nifedipine oxidation; Nootkatone; rifampin; ritonavir; saquinavir; sildenafil; simvastatin; telithromycin; terfenadine C-hydroxylation; testosterone 6 b –hydroxylation; ticlopidine; tipranavir; triazolam 4-hydroxylation triazolam; troleandomycin; verapamil.

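### Oral contraceptives are accepted in Section 22 but excluded by Section 23 read with Section 12, so a pill user's eligibility depends on which section is applied

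*Combined protocol and SAP*

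**What the plan says.** Four sections of the combined protocol and SAP bear on this point.

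- **Section 22 (acceptable birth control)** lists "oral contraceptives (e.g., combined pill or progestin only pill", then the intrauterine device, and then "shot/injection, partner uses a male condom, vaginal ring, birth control patch, and abstinence". It does not separate hormonal from non-hormonal products.
- **Section 12 (risks)** states under drug interactions: "Oral contraceptives increase Flibanserin exposures and incidence of adverse effects". The pill appears again in the list of products that may interact with the drug: "grapefruit juice, oral contraceptives, cimetidine, fluoxetine, ginkgo". The contraindications line in the same section reads "Alcohol; Moderate or strong cytochrome P450 3A4 inhibitors; Hepatic impairment" and does not name the pill.
- **Section 23 (exclusion)** bars women "Currently taking any medications that have/may have unfavorable interactions with Flibanserin" and, as a separate item, women "Under hormonal therapy". Neither item exempts contraception, and the second term is not defined.
- **Section 27 (prohibited medications)** opens with "The following medications are not to be taken by eligible subjects". The list that follows names no contraceptive, but the section refers the reader back to Section 12.

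**The concern.** Eligibility should come out the same whichever section the screener opens. Here it does not, and the drug concerned is one that the protocol itself says raises exposure and adverse effects. Screening starts with an online survey (Section 5), and precautions about contraindications are applied there (Section 8), so one rule is needed before a physician sees the woman.

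Two things are at stake. The first is safety: whether women with a stated interaction enter the trial would turn on how a screener reads the text. The second is the interpretation of Aim 2, which expects similar changes on flibanserin in premenopausal and postmenopausal women. If pill users are enrolled and most are premenopausal, the two groups would differ in drug exposure as well as in menopausal status. The outcomes include EEG, reaction times and eye movements, on which sedation could plausibly act. Section 12 reports somnolence in 11.2% on drug and 2.9% on placebo in earlier trials. The ANOVA specified in Section 11 for the behavioural data has treatment, menopausal group, stimulus type and visit as factors. It has no term for contraceptive use.

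**Working it through.** The plan gives no figure to reproduce on this point. The check is mainly a comparison of texts, followed by a sense of scale.

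**1. Oral contraceptives**

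| Section | Result for a pill user |
|---|---|
| 22 | Acceptable |
| 12, interactions | Interaction stated, with higher exposure and more adverse effects |
| 12, contraindications | Not named |
| 23, interacting medication | Excluded, because an interaction that raises adverse effects is unfavorable and the item covers even possible interactions |
| 27 | Not named; refers back to Section 12 |

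Sections 22 and 23 give opposite answers. Section 27's silence does not break the tie, because its list is not a complete version of Section 12's. Posaconazole, fluconazole and diltiazem, for example, are in the Section 12 interaction list and absent from Section 27. Absence from Section 27 therefore cannot be read as permission.

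**2. Ring, patch, injection, hormonal intrauterine device**

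Section 12 states an interaction for oral contraceptives only. These other methods are excluded only if the hormonal therapy item in Section 23 includes contraception. It could instead mean menopausal hormone treatment, which is a natural reading in a trial that admits women up to 74. The text allows both.

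**3. Scale, under assumptions**

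- Planned numbers: 60 premenopausal and 60 postmenopausal women (Section 9); 60 on each arm (Section 5).
- Assumed even cross-split: 60 × 60 / 120 = 30 premenopausal women on flibanserin. The plan does not state this figure.
- Assumed pill use among premenopausal women: 10% to 40%. The documents give no rate.
- Women whose eligibility depends on the section applied: 60 × 0.10 = 6 to 60 × 0.40 = 24.
- Of these, women on flibanserin with raised exposure: 30 × 0.10 = 3 to 30 × 0.40 = 12.

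**4. Precision of an Aim 2 comparison without pill users**

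Assume equal variance in the four treatment-by-menopausal-status cells, users evenly split between arms, and no users in the postmenopausal group. The variance of the difference between the two treatment effects is proportional to the sum of 1/n over the cells.

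- All women: 4/30 = 0.1333.
- Without 3 users per arm: 2/27 + 2/30 = 0.1407. The standard error rises by a factor √(0.1407/0.1333) = 1.03.
- Without 12 users per arm: 2/18 + 2/30 = 0.1778. The factor is √(0.1778/0.1333) = 1.15.

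The sensitivity analysis would thus have a standard error about 3% to 15% larger than the main comparison.

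**The case against.** The strongest reply is that the plan means to admit pill users. Section 22 permits them expressly, Section 12 does not list the pill as a contraindication, and Section 27 does not prohibit it. The conflict then comes from one general exclusion read through a long interaction list. This is a fair account of what may have been intended, but the Section 23 item is not limited to contraindicated or Section 27 drugs, and it makes no exception for contraception. A screener who follows it literally will exclude a woman whom Section 22 accepts.

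A second reply is that safety is watched. The interaction is disclosed in Section 12, side effects are asked about by telephone one and two weeks after Visit 1 (Section 6), orthostatic vital signs are taken at every visit (Section 13), and all adverse events are recorded (Section 28). That stands, and it reduces the consequence. It does not settle who is eligible.

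Two stronger readings are tempting, and the objections to them succeed.

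- A reader might infer that every hormonal contraceptive is both accepted and excluded. The documents do not show this. The stated interaction is for the pill only, and the hormonal therapy item is undefined.
- A reader might infer that contraceptive users can be only premenopausal and that Aim 2 is therefore biased. The postmenopausal criterion is at least 6 months without menstruation (Section 23), and no baseline laboratory tests are done (Section 13). A woman whose bleeding is suppressed by a contraceptive could be classed as postmenopausal. Users would probably be mainly premenopausal, but the documents do not make that certain.

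**Conclusion.** For oral contraceptives the contradiction is established by the text: acceptable under Section 22, excluded under Section 23 read with Section 12. The contraindications line and Section 27 add to the inconsistency and do not resolve it. Sections 7 and 19 were not available for this check. For the ring, patch, injection and any hormonal intrauterine device, the finding is an undefined term and no more.

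The consequence for Aim 2 is conditional. If pill users are enrolled, and if they fall mainly in the premenopausal group, higher exposure could confound the comparison by menopausal status. The documents give no exposure ratio, no usage rate and no effect of exposure on EEG, so the size, and even the presence, of a bias cannot be derived. The 3 to 12 women on flibanserin are a head count that rests on an assumed even split and assumed 10% to 40% use. They show a possible imbalance and do not measure a bias.

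The point should be corrected because it leaves two opposite eligibility rules on a safety-relevant interaction and is cheap to put right.

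**What to change.** 1. Reconcile Sections 12, 22, 23 and 27 so that one rule on oral contraceptives applies at screening, including in the online survey. Which rule is a clinical choice for the investigators.
2. Define hormonal therapy in Section 23 and say whether it includes contraception, so that the ring, patch, injection and hormonal intrauterine device are settled too.
3. Record contraceptive type at Visit 1.
4. If oral contraceptive users are enrolled, report adverse events by use, and repeat the Aim 2 comparison without users as a sensitivity analysis. Leave users out of both arms, so that the randomised comparison among the remaining women is kept.

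The cost is protocol wording, one baseline data item, and one sensitivity analysis with somewhat lower precision than the main comparison. No change to sample size or visits is needed.
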